8.10. Concomitant Medications or Therapies

Concomitant therapies and medications, including medications that are taken on an as needed basis and occasional therapies, will be monitored during the study. Details of prohibited medications may be found in [Section 8.10](#) of the study protocol. All concomitant medications will be coded using the WHO Drug.

The incidence of concomitant therapies and medications will be summarized using descriptive statistics by therapeutic class category, preferred base name and preferred term. Patients are counted only once in each therapeutic class, once in each preferred base name and only once in each preferred term category. Concomitant therapies and medications will include all medications taken after the first administration of the IMP up to the end of study as defined in the study protocol.

In order to determine whether a medication is concomitant, partial start dates with missing day and/or month will be imputed with the first day of the month/first month of the year, respectively and partial end dates with missing day and/or month will be imputed with the 28th day of the

month/last month of the year respectively. Imputed dates will be used for calculations only, actual dates will be listed.

Prohibited medications that are associated with QTc prolongation and prohibited antipsychotic drugs are listed in Appendix H, Tables 11 and 12, of the study protocol, respectfully. Any incidence of these prohibited medications will be listed separately.

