**8.3. Assessment of Exploratory Biomarkers**

Biomarkers are not evaluated in this study.

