Patients and/or caregivers will be instructed during the course of the study to notify the investigator if any new medication is prescribed/ administered (other than TEV-50717) or there is any change in current medications , including over-the-counter medications.	Patients and/or caregivers will be instructed during the course of the study to notify the investigator if any new medication is prescribed/administered (other than TEV-50717) or there is any change in current medications, including over-the-counter medications.	Clarification
Prohibited medications that are associated with QTc prolongation are listed in Appendix H, Table <del>11</del> 12. <del>Prohibited antipsychotic drugs are listed in Appendix H, Table 12.</del>	Prohibited medications that are associated with QTc prolongation are listed in Appendix H, Table 12.	Prohibited antipsychotic drugs table has been deleted

Protocol text with changes shown	New wording	Reason/Justification for change
5.7. Procedures for Monitoring Patient Compliance		

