Patients who participate in the study in compliance with the protocol for at least 534 weeks of treatment will be considered to have completed the study treatment . See Section 5.4 for the definition of the end of study.	Patients who participate in the study in compliance with the protocol for at least 53 weeks of treatment will be considered to have completed the treatment. See Section 5.4 for the definition of the end of study.	
5. Unscheduled Visits		

The following procedures/assessments will be performed at all in-clinic unscheduled visits:
 
 
contact IWRS
 
	
The following procedures/assessments will be performed at all in-clinic unscheduled visits:
 
 
contact IWRS
 
	

Protocol text with changes shown	New wording	Reason/Justification for change
APPENDIX H. LIST OF ALLOWED AND PROHIBITED MEDICATIONS		
Table 11: Allowed Medications		
See New wording column	
Table 11 has been revised as described below:
 
 
Added text to include dose was “anticipated to remain stable (dose and frequency) within the study duration”
 
Included additional allowed medications
 
Provided clarification around permissible use/receipt of botulinum neurotoxin (BoNT) with approval from the medical monitor.
 
Added a table note that changes to any dose required pre-approval from medical monitor
 
	Table 11 has been revised to clarify the updated expectations surrounding allowed medications in alignment with recent updates to the protocol body and inclusion/exclusion criteria
Table 12: Prohibited Antipsychotic Drugs		
Table deleted		Table 12 deleted
APPENDIX I. TOTAL BLOOD VOLUME		

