SD	Standard Deviation
SE	Standard Error
SOC	system organ class
SOP	standard operating procedure
UHDRS-TMC	Unified Huntington's Disease Rating Scale -Total Maximal Chorea
UHDRS-TMD	Unified Huntington's Disease Rating Scale -Total Maximal Dystonia
UHDRS-TMS	Unified Huntington's Disease Rating Scale - Total Motor Score
WHO	World Health Organization
α -HTBZ	alpha-dihydrotetrabenazine
β -HCG	beta-human chorionic gonadotropin
β -HTBZ	beta-dihydrotetrabenazine

INTRODUCTION

This Statistical Analysis Plan describes the planned analysis and reporting for Teva Branded Pharmaceutical Products R&D, Inc. Study TV50717-CNS-30081, An Open-Label, Long-Term Safety, Tolerability, and Efficacy Study of TEV-50717 (Deutetrabenazine) for the Treatment of Dyskinesia in Cerebral Palsy (CP) in Children and Adolescents, and was written in accordance with SOP GSD-SOP-702 (Statistical Analysis Plan).

The reader of this Statistical Analysis Plan is encouraged to read the study protocol for details on the conduct of this study, the operational aspects of clinical assessments, and the timing for completing the participation of a patient in this study.

The Statistical Analysis Plan is intended to be in agreement with the protocol, especially with regards to the primary and all secondary endpoints and their respective analyses. However, the Statistical Analysis Plan may contain more details regarding these particular points of interest, or other types of analyses (e.g. other endpoints). When differences exist in descriptions or explanations provided in the study protocol and this Statistical Analysis Plan, the Statistical Analysis Plan prevails; the differences will be explained in the Clinical Study Report (CSR).

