10. STATISTICAL SOFTWARE

All data listings, summaries, and statistical analyses will be generated using SAS® version 9.4 or later.

**11. CHANGES TO ANALYSES SPECIFIED IN THE STUDY
PROTOCOL**

Not applicable.

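### SAP 8.10 defines its separate listing of prohibited concomitant drugs through references that do not match the current protocol

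*SAP*

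**What the plan says.** SAP 8.10 makes three references to the protocol on prohibited drugs. First, "Details of prohibited medications may be found in" Section 8.10 of the study protocol. Second and third, "Prohibited medications that are associated with QTc prolongation and prohibited antipsychotic drugs are listed in Appendix H, Tables 11 and 12"; the sentence ends with a slip for the word respectively, so QTc drugs are assigned to Table 11 and antipsychotics to Table 12. It then creates an output: "Any incidence of these prohibited medications will be listed separately".

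The SAP introduction adds a precedence rule: "When differences exist in descriptions or explanations provided in the study protocol and this Statistical Analysis Plan, the Statistical Analysis Plan prevails". SAP Section 11, which is meant to record changes from the protocol's analyses, has no entries.

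**The concern.** The listing sentence makes the table references part of a specification. What they point to decides which drugs are reported as prohibited. If they point to the wrong tables, a programmer working from the SAP alone either produces a wrong listing or has to decide what was meant.

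Safety is the primary objective of this single-arm study. The listing is the SAP's only output devoted to prohibited co-medication, so its contents should agree with the rules that sites were given.

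**Working it through.** No arithmetic beyond counting applies. Setting the SAP against the current protocol:

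| SAP 8.10 reference | What the current protocol has there | Match |
|---|---|---|
| Section 8.10, details of prohibited drugs | Section 8 covers pharmacokinetics, pharmacodynamics and biomarkers; its last heading is "8.3. Assessment of Exploratory Biomarkers" | No |
| Appendix H Table 11, prohibited QTc drugs | Table of allowed medications | No |
| Appendix H Table 12, prohibited antipsychotics | Table of prohibited QTc-prolonging drugs | No |

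References correct: 0 of 3.

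**Can the intended content be recovered?** The QTc list can, because Table 12 carries that title. The antipsychotic category cannot. Table 11 permits typical and atypical antipsychotics if the dose has been stable for at least 4 weeks before entry and is expected to stay so. Only as-needed use is barred.

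**Where the numbering comes from.** The Amendment 02 log is used here only for origin, not as a conflict. Its Section 5.6 entry moves the QTc list from Table 11 to Table 12 and gives the reason "Prohibited antipsychotic drugs table has been deleted". Its Appendix H entry records the removal of "Table 12: Prohibited Antipsychotic Drugs". SAP 8.10 matches the numbering before that change. The rest of the SAP is not that old: it has the centrally read endpoints and the sample size of about 45, both of which came with Amendment 04.

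**What the listing would contain.**
- Programmed by table number: Table 11 has 5 stable-medication rows + 4 rows needing preapproval + 3 antidepressants (bupropion, fluoxetine, paroxetine) = 12 rows of allowed drugs, all shown as prohibited QTc drugs. The 10 rows of Table 12, none classed there as an antipsychotic, would be labelled antipsychotics.
- Programmed by category name: the QTc part is right, but the antipsychotic part shows permitted stable use as prohibited.
- Queried with the study team: the antipsychotic category has nothing to define it.

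**What it leaves out.** Starting a strong CYP inhibitor during the study is prohibited in protocol Sections 5.5 and 5.6, and Appendix H says the same of strong CYP2D6 inhibitors. SAP 8.10 does not mention them.

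**The case against.** The strongest reply is that this is a stale cross-reference that any careful programmer would notice, since Table 11 announces itself as the allowed list. That is likely, and the outcome might be a query or an empty category rather than a wrong listing. It does not remove the error, because the SAP would still give no definition for half of the listing.

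Other points against stand, and they limit the finding:
- **Precedence.** A reader might infer that the precedence rule turns antipsychotics into prohibited drugs. It does not. SAP 8.10 defers to the protocol and sets no rule of its own.
- **Unreported use.** A reader might infer that other prohibited drugs would go unseen. Appendix D gives use of prohibited medication as an example of an important deviation. SAP 5.9 summarises important deviations and lists all deviations, so newly started CYP inhibitors and barred as-needed use already have a route.
- **Hydroxychloroquine.** Appendix M disallows it, but that appendix lapses at sites back to regular activities, so it cannot be counted as a standing prohibition.
- **Contraindicated drugs.** MAOIs, reserpine, tetrabenazine and valbenazine have entry windows in exclusion criterion e, and no prohibition on them is repeated in Sections 5.5, 5.6 or 7.12 or Appendix H. A reader might infer that they are barred only at entry. Section 1.3.1.2 names all four as contraindicated and is not limited to entry. An MAOI antidepressant started on treatment would also fail Table 11's stability condition and need the medical monitor's preapproval. The laboratory manual's list of prohibited drugs (Section 7.5.2.2) is not among the documents. What remains is a remark on clarity.

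**Conclusion.** The point holds as an inconsistency between the SAP and the current protocol: three of three references are wrong, and one of the two categories in the listing no longer exists as a prohibition. It is worth correcting because the text defines an output, but it is minor.

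The effect is confined to one descriptive listing in about 45 patients. No estimate or test depends on it, and every drug taken on treatment still appears in the general concomitant-medication summary. The documents give no expected number of such uses, so the number of affected entries cannot be stated. A reader might go further and infer that safety conclusions are at risk or that the protocol needs amending; the documents support neither.

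The conclusion assumes that the current protocol (Amendment 04) is the one SAP 8.10 is meant to describe, which the SAP's endpoints and sample size support.

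**What to change.** Change SAP 8.10 only, before database lock (SAP 2.6.2 allows amendments until then):

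1. Cite protocol Sections 5.5, 5.6 and 7.12 and Appendix H, with its Appendix M update where that is in force. Delete the Section 8.10 citation.
2. Define the listing by Table 12 with that table's own conditions where the recorded data allow. Dose is recorded, so the azithromycin limit of 500 mg/day can be applied. Route is not among the fields named in protocol 5.6 or SAP 5.6. If it was not captured, list all clarithromycin and erythromycin use with its indication and say so, since only systemic use is prohibited.
3. Delete the prohibited-antipsychotic category.
4. Add strong CYP inhibitors newly started on treatment, stating whether the wider wording of Sections 5.5 and 5.6 (strong CYP) or the narrower wording of Appendix H (strong CYP2D6) applies.
5. Leave barred as-needed use to the deviation listing in SAP 5.9, because as-needed status is also not among the named medication fields.

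The cost is one rewritten paragraph, one respecified listing and an agreed coded list of strong CYP inhibitors, since the protocol names only three examples. No new data are needed. If lock has passed, the clinical study report can disclose the correction, as protocol Section 9 provides.

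The clarity remark on the four contraindicated drugs does not justify a protocol amendment. One would need ethics committee approval, and 42 of about 45 patients were already enrolled at Amendment 04.

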8.11. Children's Columbia-Suicide Severity Rating Scale

The frequency and severity of suicidal ideation or behavior according to the children's C-SSRS questionnaire will be presented for all patients age ≥ 12 years by visit. A shift table to examine changes in children's C-SSRS categories from baseline/screening (using the lifetime version of the questions), compared to the worst (highest) category during the treatment period will be presented by all patients and overall.

Patients will be placed into categories for suicidal ideation and suicidal behavior based on their responses to various questions. The suicidal ideation categories will be determined by the following 5 questions.

Table 10: Suicidal Ideation Category

Type	Category
Suicidal Ideation	(0) None – if response is No to Questions 1 and 2 (1) Wish to be Dead – if response to Question 1 is Yes and responses to Questions 2-5 are No. (2) Non-Specific Active Suicidal Thoughts – if response to Question 2 is Yes and response to Questions 3-5 are No. (3) Active Suicidal Ideation with Any Methods (Not Plan) without Intent to Act – if response to question 3 is Yes and response to questions 4 and 5 are No. (4) Active Suicidal Ideation with Some Intent to Act, without Specific Plan – if response to Question 4 is Yes and response to Question 5 is No. (5) Active Suicidal Ideation with Specific Plan and Intent – if response to Question 5 is Yes.

For suicidal behavior, the following categories will be used. The categories will be determined based on the response to the questions.

Table 11: Suicidal Behavior Category

Type	Category
Suicidal Behavior	
(6) Preparatory Acts or Behavior – if response to Preparatory Acts and Behavior is Yes and responses to Actual Attempt, Interrupted Attempt, Aborted Attempt, and Completed Suicide are No
 
(7) Aborted Attempt – if response to Aborted Attempt is Yes and responses to Actual Attempt, Interrupted Attempt, and Completed Suicide are No.
 
(8) Interrupted Attempt – if response to Interrupted Attempt is Yes and response to Actual Attempt, and Completed Suicide are No.
 
(9) Actual Attempt – if response to Actual Attempt is Yes and Completed Suicide is No.
 
(10) Completed Suicide - if response to Completed Suicide is Yes
 
(0) None – if responses to all the above questions are No.

Suicidal ideation or behavior will be derived as the highest suicidal ideation or behavior score at the visit. Score of 0 represent “No Suicidal Ideation/Behavior”.

The frequency and percentage of suicidal ideation, suicidal behavior, suicidal ideation or behavior, and self-injurious behavior without suicidal intent will be summarized by treatment and overall, and visit.

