i For females who are postmenarchal or  $\geq 12$  years of age. If the day 1 visit in Study TV50717-CNS-30081 is on the same day as the week 16 visit of Study TV50717-CNS-30080, the results of  $\beta$ -HCG tests in urine will be carried over from the week 16 visit. Otherwise, the  $\beta$ -HCG tests in urine will be administered at day 1.

j For females who are postmenarchal or  $\geq 12$  years of age, a  $\beta$ -HCG test in urine will be administered. A patient with a positive  $\beta$ -HCG test in urine cannot be enrolled until a  $\beta$ -HCG test in serum has been performed and is negative.

k For females who are postmenarchal or  $\geq 12$  years of age, a  $\beta$ -HCG test in serum will be administered.

l MD-CRS parts I and II assessments are done locally at the investigational center by the investigator, video recorded. In certain instances, based on the experience of the rater, certain non-physicians may be approved to rate the MD-CRS.

m Children 13 years of age and under must be interviewed in conjunction with the caregiver. For children over 13 years of age, caregiver involvement is strongly encouraged. Questions should be directed to the child, but the caregiver should be encouraged to add relevant information. The children's C-SSRS questionnaire will only be presented to patients aged  $\geq 12$  years.

n If the patient turned 12 years old during or after Study TV50717-CNS-30080, but before screening or day 1 visit of Study TV50717-CNS-30081, whichever comes first, the C-SSRS baseline/screening scale is administered. If the patient turns 12 years old during the study, C-SSRS baseline/screening will be completed as the initial assessment and the C-SSRS Since Last Visit will be completed as per [Table 5](#).

o A full CBCL assessment (Competence Scale [Parts I to VII] and a Syndrome Scale [behavioral items]) will be performed.

p Only the CBCL Syndrome Scale (behavioral items) will be performed.

q Patients and/or caregivers will be instructed during the course of the study to notify the investigator if any new medication is prescribed or if there is any change in current medications, including over-the-counter medications. Any prescribed medication should be reviewed with the investigator.

r TEV-50717 will be dispensed once all procedures and eligibility-related assessments are completed and patient eligibility is confirmed.

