## 4.2. Patient Exclusion Criteria

Patients will not be randomized/enrolled in this study if they meet any of the following criteria:

- a. Patient has clinically significant depression at screening or day 1 of this study.
  - Note: Patients receiving antidepressant therapy may be enrolled if on a stable dose for at least 6 weeks before screening or day 1 (whichever comes first) and anticipated to remain stable (dose and frequency) within the study duration.
- b. Patient has a history of suicidal intent or related behaviors based on medical or psychiatric history or the C-SSRS at screening visit, if performed, or at the day 1 visit, as applicable according to the patient's age:
  - intent to act on suicidal ideation with a specific plan, irrespective of level of ambivalence, at the time of suicidal thought
  - suicidal preparatory acts or behavior
- c. Patient has a history of a previous actual, interrupted, or aborted suicide attempt based on medical or psychiatric history or the C-SSRS at screening visit, if performed, or at the day 1 visit, as applicable according to the patient's age.
- d. Patient has a first-degree relative who has completed suicide.
- e. Patient has received any of the following concomitant medications within the specified exclusionary windows from screening or day 1 (whichever comes first) of this study:
  - within 30 days: tetrabenazine or valbenazine
  - within 21 days: reserpine
  - within 14 days: levodopa, dopamine agonists, and monoamine oxidase inhibitors
- f. Patient has received treatment with stem cells, deep brain stimulation, transmagnetic stimulation, or transcranial direct current stimulation for treatment of abnormal movements or CP since the week 15 visit of Study TV50717-CNS-30080, or the patient is not in a stable clinical condition.
- g. Patient had a surgical procedure since the week 15 visit of Study TV50717-CNS-30080 or is anticipated to have a surgical procedure during the study that, in the opinion of the investigator, makes the patient unsuitable for the study.
- h. Patient has a severe mental disability or an unstable or serious medical illness (eg, epilepsy) that, in the opinion of the investigator, could jeopardize or would compromise the patient's ability to participate in this study.

- i. Patient has a QT interval (QTc) corrected for heart rate using Fridericia's formula (QTcF) value  $>450$  msec on 12-lead ECG at screening or day 1 (whichever comes first) of this study.

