### 7.2.1. Children's Columbia-Suicide Severity Rating Scale

The children's C-SSRS assesses suicidal ideation and behaviors for all patients aged  $\geq 12$  years to determine suicide risk.

The children's C-SSRS Since Last Visit is administered at screening and/or day 1, as applicable ([Table 4](#)), and at weeks 3, 7, 14, 27, 40, 53/ET, and 54/follow-up ([Table 5](#)). However, if the patient turned 12 years old during or after Study TV50717-CNS-30080, but before screening or day 1 visit of Study TV50717-CNS-30081, whichever comes first, the C-SSRS baseline/screening scale is administered. If the patient turns 12 years old during the study, C-SSRS baseline/screening will be completed as the initial assessment and the C-SSRS Since Last Visit will be completed as per [Table 5](#).

Children 13 years of age and under must be interviewed in conjunction with the caregiver. For children over 13 years of age, caregiver involvement is strongly encouraged. Questions should be directed to the child, but the caregiver should be encouraged to add relevant information.

The children's C-SSRS is an interview by trained study personnel.

The frequency and severity of suicidal ideation or behavior according to the children's C-SSRS questionnaire will be presented by visit and by treatment group. A shift table for children's C-SSRS categories at day 1, compared to the worst (highest) category during the treatment period, will be presented.

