4.2. Specification of Baseline Values

Generally, the baseline value is the last observed data before the first dose of IMP, unless otherwise noted. If the baseline assessments occur on the same day as the first dose of IMP, it is assumed that the patients follow study procedure and those baseline assessments will be used.

The baseline assessments that will need to be performed at the initial visit for the study will be determined at the time when the patient enrolls (baseline/day 1).

Day 1: Between 1 and <2 weeks after Study TV50717-CNS-30080 week 15 visit:

To reduce patient burden and not collect duplicate information, after obtaining appropriate informed consent/assent, relevant data collected in Study TV50717-CNS-30080 will be used to provide corresponding data in this open-label study baseline/day 1 visit.

Day 1 assessments for Study TV50717-CNS-30081 that are identical to Study TV50717-CNS-30080 week 15/week 16 visit assessments, whichever is most current, **do not** need to be repeated, except for orthostatic pulse rate and blood pressure, ECG, beta-human chorionic gonadotropin (β -HCG) tests in urine, the site-administered scales, and the patient/caregiver-completed questionnaires, which need to be repeated at day 1.

Any scales/questionnaires administered at the week 16 visit for Study TV50717-CNS-30080 do not need to be repeated if the day 1 visit of Study TV50717-CNS-30081 is the same day as the week 16 visit Study TV50717-CNS-30080. See protocol Section 3 for addition details for day 1 baseline assessments.

Day 1: Between 2 and <4 weeks after Study TV50717-CNS-30080 week 15 visit:

If, in the judgment of the investigator, the patient has *not* had any clinically significant change since the week 15 visit of Study TV50717-CNS-30080 in health, concomitant medications, clinical assessments, laboratories, ECGs, or non-medical interventions, the patient will undergo all day 1 assessments outlined in [Table 2](#), except hematology, chemistry, and urinalysis laboratories and urine drug screen, which can be carried over from Study TV50717-CNS-30080 week 15 or week 16 visit, whichever is more current.

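### SAP 8.9 and 8.11 change the C-SSRS shift reference, omit two ECG outputs and redefine the QTcF thresholds set in Protocol 7.2.1 and 9.6, yet SAP Section 11 declares no change

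*SAP*

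**What the plan says.** **C-SSRS.** Protocol 7.2.1 states: "A shift table for children's C-SSRS categories at day 1, compared to the worst (highest) category during the treatment period, will be presented". Protocol 9.6 repeats this. SAP 8.11 instead takes the shift "from baseline/screening (using the lifetime version of the questions), compared to the worst (highest) category during the treatment period".

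The usual form at screening or day 1 is Since Last Visit. Protocol Table 4, footnote n, adds the baseline/screening form at entry only under this condition: "If the patient turned 12 years old during or after Study TV50717-CNS-30080, but before screening or day 1 visit of Study TV50717-CNS-30081". For younger patients, Protocol 7.2.1 says: "If the patient turns 12 years old during the study, C-SSRS baseline/screening will be completed as the initial assessment".

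SAP 4.2 gives the general rule: "Generally, the baseline value is the last observed data before the first dose of IMP". For patients who roll over within 1 to <2 weeks it adds that "relevant data collected in Study TV50717-CNS-30080 will be used to provide corresponding data in this open-label study baseline/day 1 visit". SAP 8.11 keeps a by-visit summary: "The frequency and percentage of suicidal ideation, suicidal behavior, suicidal ideation or behavior, and self-injurious behavior without suicidal intent will be summarized".

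**ECG.** Protocol 9.6 asks for ECG changes measured from the parent study's baseline. Under its general rule for continuous safety variables it also asks for change from day 1. It lists five QTcF counts: on-treatment values above 450, 480 and 500 msec, and change from day 1 above 30 and above 60 msec. SAP 8.9 plans change from baseline only. It counts confirmed QTcF above 450, 480 and 500 msec, and increases above 60 msec both as measured and as confirmed. A confirmed value is an average of up to three standard ECGs at a visit, or one summary ECG.

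**Declaration.** SAP Section 11, on changes to protocol-specified analyses, says that none apply. The SAP Introduction gives the SAP precedence over the protocol and leaves differences to be explained in the clinical study report.

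**The concern.** C-SSRS and ECG parameters are endpoints of the primary objective, long-term safety in children and adolescents. Because the SAP prevails, following it as written produces a shift table that answers a different question from the protocol's and leaves out two ECG outputs that the protocol specifies.

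The lifetime reference asks whether a patient has gone beyond their worst ever. The day 1 reference asks whether they have worsened since starting open-label drug. For ECG, patients on active drug in the parent study reach day 1 after that exposure and a washout of at least a week. For them, only the parent-study baseline precedes any trial exposure.

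Section 11 is where a reader would look for such changes. As it stands, it tells the reader that there are none and gives no prompt to explain them later.

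**Working it through.** There is no sample-size, power or error-rate figure to reproduce; the study is descriptive. The check sets the two documents side by side.

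| Output | Protocol 7.2.1 / 9.6 | SAP 8.9 / 8.11 | In SAP 11? |
|---|---|---|---|
| C-SSRS shift reference | Day 1 category | Lifetime version | No |
| ECG change | Parent-study baseline, plus day 1 under the general rule | Baseline only | No |
| QTcF change counts | >30 and >60 msec | >60 msec only | No |
| QTcF >450, >480, >500 msec | On-treatment values | Confirmed values | No |

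Four departures, none declared.

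**C-SSRS reference.** Take a patient with lifetime category 3 and day 1 category 0.
- Worst on-treatment category 3: the protocol table shows 0 to 3, a worsening. The SAP table shows 3 to 3, no shift.
- Worst on-treatment category 0: the protocol table shows 0 to 0. The SAP table shows 3 to 0, an apparent improvement.

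Where the lifetime category was fixed before dosing, the masking is confined to ideation categories 1 to 4. Exclusion b bars a history of "intent to act on suicidal ideation with a specific plan, irrespective of level of ambivalence, at the time of suicidal thought" (category 5) and of preparatory acts, and exclusion c bars previous attempts. That limit fails for a patient who completes the lifetime form on drug, because an on-drug event before the form would fall inside the reference.

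**Source of the lifetime category.** In this study the baseline/screening form goes only to patients newly reaching 12. Patients already 12 at parent-study entry receive Since Last Visit at day 1. Their lifetime category must then come from elsewhere, probably the parent study. SAP 8.11 does not say so, and the parent protocol is not among the documents.

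**ECG baseline.** SAP 4.4 makes day 1 of this study the baseline visit, with first dose on day 2. Protocol 3.1 and SAP 4.2 both require the ECG to be done at day 1. Baseline in SAP 8.9 therefore means this study's day 1 (or its screening ECG, where one was done), and the parent-study comparison is not planned.

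**QTcF change.** A rise above 30 and up to 60 msec enters no change count in the SAP. It may enter an absolute count: 425 to 465 is a rise of 465 − 425 = 40 msec and exceeds 450. It need not. A patient at or below 450 − 31 = 419 msec can rise by 31, and one at or below 450 − 60 = 390 msec can rise by 60, without exceeding 450. Such a rise would be visible only in the visit-level change statistics or, if the reading is judged abnormal, in the interpretation shifts.

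**Confirmed QTcF.** Of the protocol's five counts, one is omitted (change >30), three are redefined (>450, >480, >500) and one is kept as measured (change >60): 1 + 3 + 1 = 5. With one standard ECG at a visit, the confirmed value equals the measured value. The definitions diverge only where a visit has more than one ECG, when averaging, or substitution of a summary ECG, can bring a high reading below a threshold.

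**The case against.** The strongest reply is that departures are permitted and little is lost. Protocol Section 9 expects the SAP to carry changes, Protocol 9.10 allows them to be described in amendments, the SAP or the study report, and the SAP Introduction commits the report to explaining differences. By-visit C-SSRS frequencies, ECG change from baseline, the >60 msec counts and the interpretation shifts all remain. The study is descriptive, with about 45 patients. The choice of reference is also partly a judgement: a day 1 Since Last Visit form looks back only a short way, so recurrence of old ideation appears as a new shift. All of this stands, and it limits the weight of the point. It does not make Section 11 accurate, and it does not supply the outputs the protocol named.

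Three stronger inferences should be resisted.
- A reader might conclude that most patients have no lifetime reference. The documents show only that its source is unstated. SAP 4.2 brings parent-study data forward, and its instruction to repeat scales covers only assessments identical to those at parent week 15/16. Any count of these patients would rest on an assumed age mix and would measure a missing citation, not patients affected.
- A reader might blame the SAP for patients who turn 12 after day 1. They have no day 1 category under the protocol's own table either, so the gap belongs to both documents.
- A reader might say that a 31 to 60 msec rise disappears. It can still appear in the absolute-threshold counts, the interpretation shifts or the visit-level statistics.

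**Conclusion.** The point holds as an undeclared set of departures, and SAP Section 11 is incorrect. One shift table has a changed reference, two protocol-specified ECG outputs are missing, and three QTcF thresholds are applied to a different quantity. These should be corrected, because they serve the primary safety objective and the SAP takes precedence.

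The documents do not support saying that safety data are lost or that a signal would be hidden. The number of patients with masked ideation, or with a QTcF rise seen in no count, cannot be estimated from them and may be zero. The conclusion rests on text comparison alone. The one inference is that the lifetime category for patients already 12 at parent-study entry comes from the parent study; the finding stands whether or not that is so.

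**What to change.** 1. **SAP 8.9:** add a row for QTcF change from day 1 above 30 msec, and a table of change in ECG parameters from the parent-study baseline.
2. **SAP 8.11:** present the shift table from the day 1 category, as the protocol states. For patients newly 12 by day 1, say which items of the baseline/screening form supply that category. Keep the lifetime comparison as an added table or listing with its source named, and list separately patients with no pre-dose C-SSRS.
3. **SAP Section 11:** declare and justify every departure that is kept, including the use of confirmed QTcF.

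The cost is SAP wording, one re-based shift table, one lifetime table or listing, one ECG change table and one extra QTcF row. Day 1 C-SSRS is already collected, and the protocol already relies on parent-study ECG data, so no new assessment is needed.

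The downside is the short look-back of the day 1 Since Last Visit form. It could be about one week if the scale was given at parent week 15 and day 1 is the parent week 16 visit. Recurrence of earlier ideation will then appear as a shift, so the table should be read with the lifetime listing.
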